8.5 UNANTICIPATED PROBLEMS

8.5.1 DEFINITION OF UNANTICIPATED PROBLEMS

This study uses the Office for Human Research Protections (OHRP) definition of an unanticipated problem as any incident, experience, or outcome that meets all of the following criteria:

- 1) is unexpected, in terms of nature, severity, or frequency, given the research procedures described in the protocol and the characteristics of the study population;
- 2) is related or possibly related to participation in the research; and

3) suggests that the research places participants or others at a greater risk of harm (including physical, psychological, economic, or social harm) than was previously known or recognized.

8.5.2 UNANTICIPATED PROBLEMS REPORTING

Incidents or events that meet the OHRP criteria for unanticipated problems will prompt the study team to submit an unanticipated problem report to the IRB, which will include:

- Appropriate identifying information for the research protocol, such as the title, investigator's name, and the IRB project number;
- A detailed description of the adverse event, incident, experience, or outcome;
- An explanation of the basis for determining that the adverse event, incident, experience, or outcome represents an unanticipated problem;
- A description of any changes to the protocol or other corrective actions that are proposed in response to the unanticipated problem.

To satisfy the requirement for prompt reporting, unanticipated problems will be reported using the following timeline:

- Unanticipated problems that are serious adverse events will be reported to the IRB, Independent DSM/MSO, and NCCIH within 7 days of the investigator becoming aware of the event.
- Any other unanticipated problem will be reported to the IRB, Independent DSM/MSO, and NCCIH within 14 days of the investigator becoming aware of the problem.
- All unanticipated problems should be reported to appropriate institutional officials (as required by an institution's written reporting procedures), the supporting agency head (or designee), and OHRP within one month of the IRB's receipt of the report of the problem from the investigator.

8.5.3 REPORTING UNANTICIPATED PROBLEMS TO PARTICIPANTS

The investigative team may inform participants about other individual or aggregate level unanticipated problems if these problems have important implications for the risks associated with study participation. The decision to inform participants about unanticipated problems will be made by the investigative team with input from the IRB, the DSM, and other regulatory bodies as necessary.

If information about unanticipated problems is shared with participants who were not directly involved in the problems, then the study team will share information in such a way as to protect the confidentiality and privacy of the individuals involved.

9 STATISTICAL CONSIDERATIONS

9.1 STATISTICAL HYPOTHESES

This pilot randomized trial is designed to field-test procedures and assess the feasibility of conducting a future full-scale clinical trial. As a result, the investigators have not established any formal hypotheses about intervention efficacy or safety as part of this study. However, the study team has set benchmarks for assessing the feasibility of:

- Aim 1: Recruiting, randomizing, and retaining participants, as well as maintaining adherence to the study interventions;
- Aim 2: Successfully teaching participants to practice study-specific intervention techniques
- Aim 3: Obtaining complete and high-quality data from pain-related outcome measures.

Assessment of these benchmarks will guide future refinement of trial procedures and help the investigators assess the feasibility of eventually launching a larger-scale trial designed to collect rigorous evidence of the efficacy and safety of the yoga intervention in the target population.

9.2 SAMPLE SIZE DETERMINATION

In this pilot randomized trial is designed to assess the feasibility of and field-test procedures for a future full-scale randomized efficacy trial, a sample size of 36 participants has been selected based on consideration of the study goals as well as the time and budget constraints of the R34 funding mechanism. This pilot sample size allows for group intervention classes with an average size of 6 participants per class to be assembled for each intervention group at each of the three proposed study locations, consistent with expectations for a possible future full-scale randomized trial.

In the overall sample of 36 women, margins of sampling error (MSEs; i.e., half-widths of 95% CIs) for continuous and binary feasibility measures will be greater than 0.30 SDs and up to 15 percentage points, respectively, with the latter depending on the true proportion. Within arms, corresponding MSEs will be greater than 0.45 SDs and 20 percentage points. Given the substantial MSEs, the investigative team will take into account uncertainty about parameter estimates when drawing study conclusions.

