6.1.2 ADMINISTRATION AND/OR DOSING

Yoga practice intervention:

Instruction in the therapeutic yoga intervention will be delivered through 90-minute group classes occurring twice weekly for 8 weeks, involving a trained instructor and approximately 6 students (a.k.a. participants). The twice-weekly frequency of class instruction will allow for intensive exposure to study-specific intervention techniques to guide participants in learning to practice these techniques even if they are naïve to yoga at the start of the study.

For this pilot study, group class instruction will be delivered using the on-line video conference platform (Zoom) approved by the participating institutions. In these live Zoom-based classes, participants will be able to see, hear, and interact with their instructor and with each other in real time, and instructors will also be able to observe participants' practice of intervention techniques and provide real-time instruction through the video interface. Participants will receive mats and necessary props (i.e., yoga blocks, straps, and bolsters) to practice intervention techniques from home as they would in a public studio. In light of the video-conference format of instruction, the target class size will be 6 participants, to avoid technical challenges associated with instructors needing to observe and tailor instruction to a larger number of participants by video.

At the start of group instruction, participants in each yoga class series will attend a 90-minute orientation led by a yoga instructor who has completed in-depth study-specific training. This orientation will include an overview of the general principles of alignment-based yoga, an introduction to the structures of the pelvis, spine, and lower extremity, and a preview of the yoga props to be used. After this orientation, women will attend 90-minute group classes twice weekly for 8 weeks, led by the same instructor. During these classes, the instructor will guide women in practicing yoga postures, calling attention to ways in which they can improve pelvic floor function, and guiding women in adapting postures to overcome physical limitations.

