6.3 RANDOMIZATION AND BLINDING

Eligible women will be randomized in a 1:1 ratio to the therapeutic yoga or physical conditioning interventions, with stratification by study site. The randomization scheme will be generated by a computer algorithm using randomly permuted blocks of sizes of 2 and 4. To avoid manipulation of randomization, a statistician/analyst who is not otherwise involved in the study will prepare the randomization scheme.

When a participant is found to be eligible and willing to be randomized at the Baseline Visit, the coordinator will confirm appropriateness for randomization on the randomization assignment form in the Medrio electronic data capture system. The system will provide a randomization number corresponding to the participant's intervention assignment, consistent with the randomization scheme. Sequential randomization numbers will provide a check on the validity of randomization, and the system will be configured to prevent reversal or manipulation of randomization.

Although there is no effective way to completely blind participants in this trial to their intervention assignment, study procedures will preserve the blinding of investigators and staff involved in abstracting or analyzing outcomes. Only study personnel who are directly responsible for randomizing participants, administering interventions, or promoting adherence to interventions will be aware of intervention assignment. All personnel involved in abstracting, assessing, or analyzing pain-related outcomes will remain blinded until all participants have completed the final visit, trial data are edited and cleaned, and the dataset is locked.

The Medrio electronic data capture system will be programmed to hide information about intervention assignment from study investigators or staff who are required to remain blinded. Only study personnel who are required to remain unblinded will be given user rights in the Medrio system that allow them to view the intervention assignments for individual participants.

To minimize differential expectations of success between groups, participants will be told that they are participating in a study of two types of low-impact physical activity programs and that the investigators do not know which intervention is more effective for the management of chronic pelvic pain (which is true). While awareness of group

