For these aim 1 outcomes, the investigative team has set benchmarks of randomizing at least 50% of women who undergo screening visits. Participant drop-out rates of <15%, 15-25%, and >25% will be interpreted as indicating optimal, acceptable, and inadequate retention, respectively. Among non-dropouts, completion of >85%, 75-85%, and <75% of group classes and home practice hours will be considered to indicate optimal, acceptable, and inadequate adherence, respectively.

Although the main analyses to assess the feasibility of recruitment, retention, and adherence will rely on descriptive statistics, the investigative team may generate 95% confidence intervals (CIs) to explore the precision of these performance estimates if this is deemed useful to guide planning for a future randomized trial.

9.4.3 MAIN ANALYSES TO ADDRESS AIM 2

Analyses to assess the feasibility of teaching participants to practice their assigned interventions will focus on data obtained from a) participant questionnaires assessing their confidence in performing yoga or physical conditioning techniques according to protocol (i.e., self-efficacy in performing postures/exercises), and b) expert consultants' observations of participants' competence in performing these techniques (i.e., observed competence in performing postures/exercises). Participants will rate their self-confidence in performing each posture/exercise on a 5-point Likert scale (5-extremely, 4-very, 3-moderately, 2-somewhat, and 1-not at all confident). Expert consultants will observe and rate participants' success in performing each posture/exercise on a 5-point Likert scale (5-extremely, 4-very, 3-moderately, 2-somewhat, and 1-not at all confident).

Using data from the 8-week yoga posture self-efficacy questionnaires, the investigators will examine the percentage of participants completing the yoga intervention program who demonstrate at least moderate self-efficacy in performing postures, based on an average posture self-confidence/self-efficacy rating of 3 or higher ("Percentage of participants with at least moderate self-efficacy in performing yoga postures at 8 weeks").

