In recognition of potentially important differences in data completion, quality, or distribution, the investigative team may also pursue a limited set of analyses stratified by clinical recruitment site (i.e., San Francisco, Oakland, and Palo Alto, each of which will be the focus of a different intervention wave). This may alert investigators to gross variation or clustering across sites which could complicate a future multisite trial.

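### Section 9.2 computes its margins of error as if the women were independent, although post-randomization outcomes arise in six shared classes; positive within-class correlation would make those margins too small

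*Combined protocol and SAP*

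**What the plan says.** Section 9.2 reports that "a sample size of 36 participants has been selected" in view of the study goals and the limits of time and budget. It explains that this number allows "group intervention classes with an average size of 6 participants per class to be assembled for each intervention group" at each of three locations. With two arms and three locations, that makes six classes, three per arm.

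The next paragraph turns to precision: "In the overall sample of 36 women, margins of sampling error (MSEs; i.e., half-widths of 95% CIs) for continuous and binary feasibility measures" are given as more than 0.30 SD for continuous measures and at most 15 percentage points for binary ones, the latter depending on the true proportion. Within arms the margins are given as more than 0.45 SD and 20 points. The section calls these margins substantial and undertakes to allow for uncertainty when drawing conclusions. It mentions no ICC, design effect or effective sample size.

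Section 6.1.2 describes the shared exposure. In the yoga arm, after an orientation, "women will attend 90-minute group classes twice weekly for 8 weeks, led by the same instructor". The control arm runs to the same format, with one therapist or trainer per class.

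Section 9.4.2 says that "the investigative team may generate 95% confidence intervals (CIs) to explore the precision of these performance estimates" where this seems useful. Sections 9.4.3 and 9.4.4 contain similar optional provisions. None names an interval method or mentions class.

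Clustering appears only in Section 9.4.6 C, as optional work: within-site ICCs of the pain-related measures, and analyses stratified by site, of which it says "This may alert investigators to gross variation or clustering across sites which could complicate a future multisite trial".

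**The concern.** Women in one class share an instructor, a timetable and a peer group for 16 sessions, and Section 4.3 intends the live format to build mutual support among them. Drop-out, class attendance, self-efficacy and rated competence are all recorded after that exposure. A popular or unpopular instructor, or an awkward time slot, can move several women in the same direction. In that case 36 women carry less information than 36 independent observations, and a half-width computed from n = 36 or n = 18 is too small.

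What is at stake is how the retention, adherence and teaching results are read. Section 9.2 undertakes to weigh uncertainty, and the published margins tell the reader how much uncertainty there is. If they leave out a source of variation built into the design, that undertaking rests on too small a figure.

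**Working it through.** **Inputs from the documents.** Total of 36 and 95% confidence (Section 9.2). "Eligible women will be randomized in a 1:1 ratio" (Section 6.3), hence 18 per arm. Classes of about 6, three locations, two arms (Section 9.2). A 75% benchmark for self-efficacy and rated competence (Section 9.4.3). Section 9.4.2 also uses 75% as the lower limit of acceptable adherence and 25% as the upper limit of acceptable drop-out. Since p(1−p) is the same at 25% and 75%, one half-width serves both.

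**Assumed, because the documents give no value:** class-level ICC of 0.01, 0.05 or 0.10.

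**Step 1: reproduce the stated margins under independence.**
- Continuous: 1.96/√n gives 1.96/√36 = 0.327 SD and 1.96/√18 = 0.462 SD. These agree with the stated floors of 0.30 and 0.45.
- Binary: 1.96 × √(p(1−p)/n). With n = 36 and p = 0.70: 1.96 × √(0.21/36) = 15.0 points. With n = 18 and p = 0.75: 1.96 × √(0.1875/18) = 20.0 points.

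The stated figures are therefore consistent with simple-random-sample half-widths, with no allowance for clustering.

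**Step 2: allow for classes of 6.** Design effect = 1 + (6 − 1) × ICC. Each half-width is multiplied by the square root of the design effect.

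| Assumed class ICC | Design effect | Multiplier | Effective n (overall / arm) | Overall, p = 75% | Within arm, p = 75% | Overall, SD | Within arm, SD |
|---|---|---|---|---|---|---|---|
| 0 | 1.00 | 1.000 | 36 / 18 | 14.1 | 20.0 | 0.327 | 0.462 |
| 0.01 | 1.05 | 1.025 | 34.3 / 17.1 | 14.5 | 20.5 | 0.335 | 0.473 |
| 0.05 | 1.25 | 1.118 | 28.8 / 14.4 | 15.8 | 22.4 | 0.365 | 0.516 |
| 0.10 | 1.50 | 1.225 | 24.0 / 12.0 | 17.3 | 24.5 | 0.400 | 0.566 |

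Binary half-widths are in percentage points.

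**Step 3: find where the 15-point ceiling gives way at 75%.** Set 1.96 × √(0.1875 × DE/36) = 0.15. Then DE = (0.15/1.96)² × 36/0.1875 = 1.125, and ICC = (1.125 − 1)/5 = 0.025. Below about 0.025 the ceiling holds at this benchmark. Above it, the ceiling fails.

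**Step 4: separate this from another issue.** The ceiling already fails under independence for true proportions between about 30% and 70%. At 50% the half-width is 1.96 × √(0.25/36) = 16.3 points. That is a matter of which proportion is used, not of clustering. The comparison above is made at 75% because there the ceiling holds under independence, so any breach is due to the class effect alone.

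**Step 5: effect on an unadjusted interval.** In the normal approximation, a nominal 95% interval that ignores class covers with probability 2Φ(1.96/√DE) − 1. This is 94.4%, 92.0% and 89.0% at ICCs of 0.01, 0.05 and 0.10.

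**The case against.** Much of the case on the other side stands.

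- **Three of the four margins are floors.** Clustering makes them larger, which is consistent with a statement that they exceed some value. A reader might infer that all the stated precision is wrong. The wording does not support that: only the 15-point ceiling can be contradicted.
- **The sample size does not depend on these margins.** Section 9.2 bases 36 on goals, time, budget and the assembly of classes. An inference that the trial is too small does not follow.
- **No decision rule uses a confidence interval.** The composite in Section 9.4.5 is a count, at least 24 women, and no interval is planned for it. The other benchmarks are point thresholds. A reader might infer that the decision on a full-scale trial is invalidated, but nothing in the documents ties it to interval width.
- **Not every interval is affected.** The share of screened women who are randomized is settled before classes begin, so it has no class effect.
- **The plan looks at clustering.** With one site as the focus of each wave and about 6 women per arm per wave, site within arm is close to class. But that work is optional, its ICCs concern pain-related measures, and none of it feeds back into the margins or intervals. It also falls short of saying that the plan expects clustering; it says only that these analyses might reveal it.
- **The size is assumed.** At an ICC of 0.01 the overall change is 0.4 points. Correlation may be weaker for measures completed alone at home, such as pain logs and home practice. Loss of coverage also depends on the method and the proportion: an exact beta-binomial calculation for an unadjusted Wilson interval at n = 36 and 75% gives 94.5% and 92.0% at ICCs of 0.05 and 0.10, nearer nominal than the approximation in Step 5.

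What remains is that a stated numerical ceiling assumes independence without saying so, in a design that makes independence doubtful.

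**Conclusion.** The point holds in a limited, conditional form. The margins in Section 9.2 carry no allowance for six shared classes of about 6. If women within a class are positively correlated, the margins for class-dependent post-randomization measures are understated by a factor of √(1 + 5 × ICC): about 2%, 12% or 22% at assumed ICCs of 0.01, 0.05 or 0.10. At the plan's 75% benchmark, the stated maximum of 15 points survives an ICC of 0.01 but fails once the ICC passes about 0.025.

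The conclusion rests on an ICC that the documents do not supply, on equal classes of 6, and on all 36 women contributing. It bears on how precisely the feasibility rates are reported. It does not bear on the randomization yield, the composite benchmark or the choice of 36.

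**What to change.** In Section 9.2, say that the present margins assume independent participants. For measures taken after randomization, restate them with design effect 1 + 5 × ICC at assumed class ICCs of 0.01, 0.05 and 0.10, name the proportion used, and remove the 15-point maximum. Suitable wording would be: *With classes of about 6 and assumed class ICCs of 0.01 to 0.10, 95% half-widths at a true proportion of 75% are about 14.5 to 17.3 points overall and 20.5 to 24.5 points within arms; for continuous measures they are about 0.335 to 0.400 SD overall and 0.473 to 0.566 SD within arms.*

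In Sections 9.4.2 to 9.4.4, add one line: any 95% CI for a post-randomization outcome will be shown unadjusted, with a sensitivity version widened over the same ICC range. A range is preferable to one fixed ICC, which the documents could not justify. It is also more practical than cluster-robust intervals: three classes per arm leave 2 degrees of freedom and a t multiplier of 4.30.

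Leave the interval for the randomization yield and the count benchmark of 24 as they are.

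The cost is a few sentences, with no added participants, visits or data. The drawback is that the stated margins become somewhat wider and depend on an assumed ICC.

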9.3 POPULATIONS FOR ANALYSES

Selection of participants for inclusion in analyses will depend on the endpoints involved. Specifically:

- Analyses addressing the feasibility of recruitment will focus on the total number of women responding to recruitment advertisements, as well as the smaller subset of women who provide informed consent at the Screening Visit.
- Analyses addressing the feasibility of retention in the 8-week intervention period will focus on participants who are randomized to an intervention group, even if these participants do not go on to complete recommended intervention sessions.

Analyses of the feasibility of retention in the post-intervention follow-up phase will focus on participants who complete the 8-week intervention programs.

- Analyses addressing adherence to study intervention classes and home practice will focus on the subpopulation of participants who complete their 8-week intervention programs. In the case of adherence to post-intervention practice, analyses will focus on the subpopulation of participants who complete the additional post-intervention follow-up period.
- Analyses addressing the feasibility of teaching participants to practice intervention techniques will focus on participants who: 1) are randomized to one of the two intervention programs, and 2) do not withdraw early from their assigned 8-week intervention program. Participants will be included in analyses even if they miss one or more intervention classes or do not complete home intervention practice.
- Analyses addressing completeness of pain measure outcomes data will focus on participants who are randomized to an intervention group and who complete: a) the 8-week intervention portion of the study (for assessment of completeness of 8-week pain outcomes data), and b) the 8-week post-intervention follow-up visit (for assessment of 8-week post-intervention follow-up pain outcomes data).

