9.4 STATISTICAL ANALYSES

9.4.1 GENERAL APPROACH

For descriptive statistics, categorical variables will be presented as frequency counts and percentages. Continuous variables will be presented as means and standard deviations. If on visual inspection of q-q plots, distributions deviate significantly from normality continuous variables will also present median and interquartile range.

Where needed, inferential statistics will be generated using Chi-square tests, Fisher's exact tests, or t-tests as appropriate. If outcome variable distributions deviate significantly from normality then comparisons will be made using the Mann-Whitney U test .

9.4.2 MAIN ANALYSES TO ADDRESS AIM 1

Analyses to assess the feasibility of participant recruitment, retention, and adherence to interventions will use data obtained from study visit and randomization logs, intervention class attendance logs, and home intervention practice logs, primarily during the baseline and 8-week intervention period.

Feasibility of recruitment will be assessed by examining the proportion of participants who attend a Screening Visit who go on to be randomized ("Percentage of screenees who are eventually randomized").

Feasibility of participant retention during the intervention phase of the research will be assessed by examining the proportion of randomized participants in each intervention

arm who drop out before the 8-week visit ("Percentage of randomized participants who drop out by 8 weeks, by intervention arm").

Feasibility of promoting participant adherence to group intervention classes will be assessed by examining the percentage of non-dropout participants in each intervention arm who complete at least 75% of recommended group classes during the 8-week intervention period ("Percentage of non-drop-outs completing at least 75% of intervention classes over 8 weeks, by intervention arm").

Feasibility of promoting adherence to home intervention practice will be assessed by examining the percentage of non-dropout participants in each arm who complete at least 75% of recommended home practice hours during the 8-week intervention period ("Percentage of non-drop-outs completing at least 75% of home intervention practice over 8 weeks, by intervention arm").

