Among participants completing the 8-week intervention programs, the investigative team will examine the percentage who complete 7-day pain severity/intensity measures 8 weeks, either within or outside of recommended time windows ("Percentage of expected pain logs returned at 8 weeks"). The investigators will also examine the percentage of participants who complete pain interference questionnaires at 8 weeks ("Percentage of expected pain interference questionnaires returned at 8 weeks") and pelvic pain impact measures at 8 weeks ("Percentage of expected pelvic pain impact measures returned at 8 weeks").

The investigative team anticipates that over 90% of pain severity/intensity, interference, and impact measures anticipated at 8 weeks will be completed and returned. Additionally, the investigators anticipate that over 75% of these measures will be completed and returned within recommended time windows.

If rates of return of the above outcome measures at 8 weeks are adequate, the investigators will also examine the mean (and/or median) and standard deviation (and/or interquartile range) of change in pain severity/intensity, interference, and impact scores over 8 weeks. This may guide future efforts to identify well-behaved and relatively precise pain-related outcome measures for use as primary and secondary efficacy outcomes in a future full-scale efficacy trial.

Analyses will focus on the combined sample of participants reaching the 8-week timepoint, although further analyses may be performed to explore differences between intervention arms if the completeness or quality of outcomes data at 8 weeks is lower than expected. Additionally, investigators may generate 95% CIs to explore the precision of estimates if deemed useful to guide future trial planning.

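### Section 9.2 states precision for 36 women and 18 per arm with no drop-out allowance, so its 15-point ceiling is not met for the completer-based Aim 3 outcome judged against 75%

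*Combined protocol and SAP*

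**What the plan says.** Section 9.2 chooses 36 women on study goals, class size, time and budget, then describes precision. "In the overall sample of 36 women, margins of sampling error (MSEs; i.e., half-widths of 95% CIs) for continuous and binary feasibility measures" are described by one lower bound (continuous) and one ceiling (binary): the section says that they "will be greater than 0.30 SDs and up to 15 percentage points, respectively, with the latter depending on the true proportion". By arm, the margins are put above 0.45 SD and 20 points. The section calls the margins substantial and commits the team to weighing uncertainty in its conclusions.

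The analysis populations are set elsewhere and differ by outcome:

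- **Recruitment (9.4.2).** "Feasibility of recruitment will be assessed by examining the proportion of participants who attend a Screening Visit who go on to be randomized". The benchmark is at least 50%.
- **8-week drop-out (9.3, 9.4.2).** All randomized women, by arm. "Participant drop-out rates of <15%, 15-25%, and >25% will be interpreted as indicating optimal, acceptable, and inadequate retention, respectively".
- **Adherence (9.3, 9.4.2).** "Analyses addressing adherence to study intervention classes and home practice will focus on the subpopulation of participants who complete their 8-week intervention programs". Results are by arm.
- **Teaching success, Aim 2 (9.3, 9.4.3).** Women who do not withdraw early, separately for each programme, with an expectation of over 75%.
- **Data completeness and pain change, Aim 3 (9.4.4).** "Analyses will focus on the combined sample of participants reaching the 8-week timepoint". The expectations are over 90% returned, and over 75% returned within the time window.
- **Primary composite (9.4.5).** At least 24 of the randomization target of 36.

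**The concern.** The margins in 9.2 are computed at full enrolment, yet the plan itself treats 15-25% drop-out as acceptable and restricts several main outcomes to women still in the programme at 8 weeks. For those outcomes the stated precision belongs to a larger group than the one analysed.

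This matters because confidence intervals for the results are optional in 9.4.2 to 9.4.4. The figures in 9.2 are therefore the only ones fixed in advance for judging how firmly the 75% and 90% expectations are met, and those judgements feed the decision on a full-scale trial.

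**Working it through.** **Inputs.** Two-sided 95% intervals, z = 1.96, and N = 36 (9.2). 1:1 allocation (6.3), hence 18 per arm; the 18 is derived, not stated. Drop-out bands (9.4.2). Benchmarks of 50% (9.4.2), 75% (9.4.3, 9.4.4), 90% (9.4.4) and 24/36 (9.4.5).

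**Formulas.** Binary (Wald): 1.96 × √(p(1−p)/n). Continuous, in SD units: 1.96/√n.

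**Reproducing the plan's figures.**

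- N = 36: 1.96/√36 = 0.327 SD. Binary: 16.3 points at p = 0.5, 15.0 at 0.70, 14.1 at 0.75, 9.8 at 0.90.
- N = 18: 1.96/√18 = 0.462 SD. Binary: 23.1 points at p = 0.5, 20.0 at 0.75.

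The stated 0.30 SD, 0.45 SD and 20 points match 36 and 18 with no attrition. The 15-point ceiling holds at N = 36 only for p at or above about 0.70, or at or below about 0.30.

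**Numbers analysed, in whole women.**

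- Combined: 36 × 0.85 = 30.6 and 36 × 0.75 = 27. Drop-outs of 6 to 9 (16.7% to 25.0%) leave 27-30.
- Per arm: 18 × 0.85 = 15.3 and 18 × 0.75 = 13.5. Drop-outs of 3 or 4 (16.7%, 22.2%) leave 14-15.
- Under 15% drop-out: at most 5 overall and 2 per arm, leaving 31-36 and 16-18.

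Each count is taken within the band on its own.

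**Half-widths (Wald; z for continuous).**

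| n | SD units | p = 0.5 | p = 0.75 | p = 0.90 |
|---|---|---|---|---|
| 36 | 0.327 | 16.3 | 14.1 | 9.8 |
| 31 | 0.352 | 17.6 | 15.2 | 10.6 |
| 30 | 0.358 | 17.9 | 15.5 | 10.7 |
| 27 | 0.377 | 18.9 | 16.3 | 11.3 |
| 18 | 0.462 | 23.1 | 20.0 | 13.9 |
| 15 | 0.506 | 25.3 | 21.9 | 15.2 |
| 14 | 0.524 | 26.2 | 22.7 | 15.7 |

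The widening is √(36/30) = 1.10 to √(36/27) = 1.15 combined, and √(18/15) = 1.10 to √(18/14) = 1.13 per arm.

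**Where the ceiling binds.** Solving p(1−p) = n × (0.15/1.96)² for p above 0.5, the half-width is 15 points or less only when p is at least 0.70 (n = 36), 0.77 (n = 30) or 0.80 (n = 27). The 75% benchmark passes at 36 and fails at 27-30.

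**Interval method.** At 75% the Wilson half-width is 13.7 (n = 36), 14.9 (n = 30) and 15.6 (n = 27). The exact half-width is 15.0 for 27/36 and 17.6 for 20/27. So the breach at the lower end of the drop-out band depends on the method, which 9.2 does not name.

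**Recruitment.** 36/0.50 = 72 screenees if the benchmark is just met: 1.96 × √(0.25/72) = 11.5 points, narrower than stated.

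**The case against.** Three of the four figures in 9.2 are lower bounds. With 27-30 combined the continuous margin is 0.36-0.38 SD, still above 0.30. With 14-15 per arm the margins are 0.51-0.52 SD and 21.9-22.7 points at 75%, still above 0.45 SD and 20 points. A smaller n does not make these statements false. This stands; the only loss is that they are less informative.

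A reader might infer that none of the stated margins fits any analysis. The documents do not support that. The main drop-out analysis uses all 18 randomized per arm, the primary composite is judged against 36, and section 3 also plans retention in the overall sample.

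A reader might also set 18.9 points against the 15 and blame drop-out for the gap. But 18.9 is the p = 0.5 value at n = 27. No Aim 3 benchmark sits at 50%, and at p = 0.5 the ceiling already fails at n = 36 (16.3), which is a separate matter from attrition. Nor does the 90% return benchmark breach the ceiling.

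Three further points have weight. Section 9.2 is a planning statement, and the optional intervals in 9.4 would use the actual denominators. Section 7.2 lets randomized but untreated women be replaced, which could offset some loss to an unstated extent. The sample size was not chosen for precision. These limit the importance of the point, but they do not make the 15-point figure right for Aim 3.

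**Conclusion.** The point holds in a limited form. Section 9.2 makes no drop-out allowance, while adherence, Aim 2 and Aim 3 are analysed in women who remain. One stated figure fails as a result: the overall ceiling of 15 points, for Aim 3 return within the time window at 75%. There the half-width is 15.5-16.3 points, that is 0.5-1.3 points over, against 14.1 at full enrolment. The other figures stay true at the 75% benchmark but understate how wide the margins would be, by about 10-15%.

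This is a correction to the reported precision. It is not a design flaw and gives no ground for calling the sample too small.

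Assumptions: drop-out within the 15-25% band, 36 randomized with 18 per arm, no replacement, independent women, and Wald intervals. Under 15% drop-out the gap shrinks: the half-width at 75% runs from 14.1 (n = 36) to 15.2 (n = 31).

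**What to change.** In 9.2, replace the 36/18 statement with half-widths at each outcome's own denominator, and name the interval method. On the Wald basis:

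- **Recruitment yield:** about 11.5 points at 50%, assuming 72 screenees.
- **Drop-out:** n = 18 per arm; 16.5 points at 15% and 20.0 at 25%.
- **Adherence and Aim 2:** n = 14-15 per arm; about 22-23 points at 75%.
- **Aim 3:** n = 27-30 combined; 15.5-16.3 points at 75%, 10.7-11.3 at 90%, and 0.36-0.38 SD for pain change.
- **Primary composite:** n = 36; 15.4 points at 24/36.

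Show the under-15% drop-out case beside these (31-36 combined, 16-18 per arm). Drop the 15-point ceiling or restate it for the completer numbers; the maximum at p = 0.5 is 17.9-18.9 points for n = 30-27.

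The cost is a few lines of text and a slightly less favourable stated precision. Enrolment, procedures and benchmarks are unchanged.
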